## 17.4. PHARMACODYNAMIC ANALYSIS

The PD variables of interest are change from baseline in PANSS total score.

If one PANSS item is missing, it will not be imputed. If one or more items are missing at a specific Document:

Author:

Version Number:  
 Version Date:

Final Draft  
 11APR2019

Template No: CS\_TP\_BS016 Revision 4  
 Effective Date: 01Apr2016

Reference: CS\_WI\_BS005

visit, the total score will be set to missing at that visit.

#### **17.4.1. EXPLORATORY PHARMACODYNAMIC VARIABLES & DERIVATIONS**

The PANSS is an interview-based measure of the severity of psychopathology in adults with psychotic disorders. The measure is comprised of 30 items and 3 scales: The Positive subscale assesses hallucinations, delusions, and related symptoms; the Negative subscale assesses emotional withdrawal, lack of motivation, and similar symptoms; and the General Psychopathology subscale addresses other symptoms such as anxiety, somatic concern, and disorientation.

- The Positive subscales consist of the following items:
  1. Delusions
  2. Conceptual disorganization
  3. Hallucinatory Behavior
  4. Excitement
  5. Grandiosity
  6. Suspiciousness/persecution
  7. Hostility.
- The Negative subscales consist of the following items:
  1. Blunted Affect
  2. Emotional Withdrawal
  3. Poor Rapport
  4. Passive apathetic social Withdrawal
  5. Difficulty in abstract thinking
  6. Lack of spontaneity and flow of conversation
  7. Stereotyped thinking.

---

Document:

Author:

Version Number:  
Version Date:

Final Draft  
11APR2019

Template No: CS\_TP\_BS016 Revision 4  
Effective Date: 01Apr2016

Reference: CS\_WI\_BS005

- The General Psychopathology subscale consists of the following items:
  1. Somatic concerns
  2. Anxiety
  3. Guilt Feelings
  4. Tension
  5. Mannerism and posturing
  6. Depression
  7. Motor retardation
  8. Uncooperativeness
  9. Unusual thought content
  10. Disorientation
  11. Poor attention
  12. Lack of judgment and insight
  13. Disturbance of volition
  14. Poor impulse control
  15. Preoccupation
  16. Active social avoidance

An anchored Likert scale from 1 to 7, where values of 2 and above indicate the presence of progressively more severe symptoms, is used to score each item. 30 Individual items are then summed to determine a total score.

Of the 30 items included in the PANSS, 7 constitute a Positive Scale, 7 a Negative Scale, and the remaining 16 a General Psychopathology Scale. The scores for these scales are arrived at by summation of ratings across component items. Therefore, the potential ranges are 7 to 49 for the Positive and Negative Scales, and 16 to 112 for the General Psychopathology Scale, where PANSS

---

Document:

Author:

Version Number:  
Version Date:

Final Draft  
11APR2019

Template No: CS\_TP\_BS016 Revision 4  
Effective Date: 01Apr2016

Reference: CS\_WI\_BS005

total score ranges from 30-210.

#### **17.4.2. MISSING DATA METHOD FOR THE PHARMACODYNAMIC VARIABLE**

The PANSS total score will be set to missing if any one item is missing.

#### **17.4.3. ANALYSIS OF PHARMACODYNAMIC VARIABLES**

The PD variable is change from baseline in PANSS total score.

Pharmacodynamic population will be used for the exploratory analysis.

Summary statistics (n, mean, SD, median, min, and max) for actual values and change from baseline in PANSS Total Score will be presented by visit and treatment (dose level of Lurasidone injectable suspension and pooled placebo).

Additionally, the PANSS score for each item, subscale scores and total score will also be listed.

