Dose proportionality of Lurasidone injectable suspension will be assessed using a power model for C_{max} , AUC_{0-last} , and AUC_{0-inf} of Lurasidone injectable suspension with a formula of ln (PK parameter) = $\alpha + \beta \cdot ln$ (dose level).

The estimate of the slope (β) , together with its 90% confidence interval (CI) will be calculated from the model. Dose proportionality assessment will be performed for the dose range studied.

Pharmacodynamic (PD) Analyses

The pharmacodynamic variable is change from baseline in PANSS total score. The pharmacodynamic variable will be analyzed by mixed model for repeated measures (MMRM) method. The MMRM model will include treatment, time, baseline score, and treatment-by-time interaction.

Sample Size:

There will be no formal estimation for the sample size as no previous human PK data are available for Lurasidone injectable suspension and the primary endpoints are safety. The sample size of 8 subjects per cohort (6 Lurasidone injectable suspension subjects and 2 placebo subjects) is selected based on clinical and practical considerations for a study of this design.

Table 2: Schedule of Assessments

Study Period	Screen	Wash	nout/Taper ^a		Treatment/Observation ^a				Re	Follow-up						
Study Day	-35 to -13	-12	-11 to -9	-8	-7	-6	-5 to -1	1	2-8	9-14	15	22	29	30-32	33	61 ± 2
Procedures/Assessments																
Obtain Informed Consent	X															
Review Inclusion/	X			X												
Exclusion Criteria																
Record Medical and	X															
Psychiatric History																
Record Demographics	X															
Perform Physical	X	X		X							X		X		X	X
Examination																
Record Height	X															
Record Weight and BMI	X			X									X		X	X
Obtain Vital Sign	X	X		X	X	X	X	X	X	X	X	X	X		X	X
Measurements ^b																
Perform 12-Lead ECG ^c	X	X		X	X	X		X	X	X	X	X	X		X	X
Clinical Laboratory Tests ^d	X			X				X	X		X	X	X		X	X
Serum Prolactine	X			X				X	X		X	X	X		X	X
Serology	X															
Serum Pregnancy Test	X	X		X									X			
(females)																
Urine Drug Screen	X	X		X									X			
Urine Alcohol Test	X	X		X									X			
Blood Samples for PK ^f					X	X		X	X		X	X	X			X
Urine Samples for PK ^g								X	X							
Psychotropic Medications ^{h,i}		X											X	X	X	
Administer	X			X	X		X	X	X		X	X	X		X	X
Columbia-Suicidality																
Severity Rating Scale																
(C-SSRS) ^j																
Administer Positive and	X				X			X	X		X	X	X			

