14.3.7. Pharmacodynamic Analyses

The pharmacodynamic variable is change from baseline in PANSS total score. The pharmacodynamic variable will be analyzed by mixed model for repeated measures (MMRM) method. The MMRM model will include treatment, time, baseline score, and treatment-by-time interaction. Details will be provided in the SAP.

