14.3.9. Treatment of Missing Data

For analyses of change from baseline, baseline will generally be defined as the predose assessment on Day 1 as scheduled. If this value is unavailable, the last non-missing value prior to dosing will be used. Otherwise, missing observations will be treated as missing at random, and no data imputation will be performed.

Details of incomplete/missing dates for any endpoint will be provided in the SAP.

15. PROCEDURE FOR CLINICAL STUDY QUALITY CONTROL/ DATA COLLECTION, MANAGEMENT, AND QUALITY ASSURANCE

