### **3.3.3. PHARMACODYNAMIC ENDPOINT**

Change from baseline, and placebo-corrected change from baseline in PANSS total score.

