## 4.7. CHANGES TO ANALYSIS FROM PROTOCOL

There were no changes in the analyses or definitions planned in the protocol.

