## 7.5. STATISTICAL TESTS

90% CIs will be used for the PK analysis.

---

Document:

Author:

Version Number:  
Version Date:

Final Draft  
11APR2019

Template No: CS\_TP\_BS016 Revision 4  
Effective Date: 01Apr2016

Reference: CS\_WI\_BS005

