## 7.8. MISSING DATA

Missing PK data will be handled as described in Section 17 of this analysis plan.

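### The SAP drops the protocol's MMRM for PANSS and describes no placebo-corrected estimate, yet states that no planned analysis changed

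*SAP*

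**What the plan says.** **Protocol.** The synopsis states: "The pharmacodynamic variable will be analyzed by mixed model for repeated measures (MMRM) method". Section 14.3.7 repeats this and gives the fixed effects: "The MMRM model will include treatment, time, baseline score, and treatment-by-time interaction". It leaves the remaining details to the SAP. Section 14.3.9 adds the missing-data assumption: "Otherwise, missing observations will be treated as missing at random, and no data imputation will be performed". Section 5.3 makes both the change from baseline and its placebo-corrected version the pharmacodynamic endpoint.

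**SAP.** Section 3.3.3 keeps that endpoint: "Change from baseline, and placebo-corrected change from baseline in PANSS total score". The analysis in section 17.4.3 is descriptive, tabulated at each visit for every dose and for pooled placebo: "Summary statistics (n, mean, SD, median, min, and max) for actual values and change from baseline in PANSS Total Score will be presented". It also lists item, subscale and total scores (Listing 16.2.6.2). The one PANSS results table in Appendix 4 is Table 14.2.5, whose title covers actual values and change from baseline by timepoint and treatment. Section 7.5, on statistical tests, says only: "90% CIs will be used for the PK analysis". Section 4.7 states: "There were no changes in the analyses or definitions planned in the protocol".

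**The concern.** The protocol names the SAP as the place where the PANSS model is to be completed. The SAP instead omits the model and certifies that nothing changed. It also carries forward an endpoint, placebo-corrected change, for which its text describes no analysis.

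Two things are at stake. If no model is run, an analysis fixed in the protocol disappears without being declared. If one is run later, its covariance structure, degrees-of-freedom method and confidence level are fixed in neither document and could be chosen with treatment assignments known. PANSS is a stated objective of the study and its only pharmacodynamic endpoint, so the departure should be visible.

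**Working it through.** **1. The texts side by side**

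| Element | Protocol | SAP |
|---|---|---|
| Endpoint | Change, and placebo-corrected change (5.3) | Same (3.3.3) |
| Method | MMRM (synopsis, 14.3.7) | By-visit summary statistics and a listing (17.4.3) |
| Fixed effects | Treatment, time, baseline score, treatment-by-time (14.3.7) | None |
| Covariance, df method, CI level | Left to the SAP | Not given; 7.5 covers PK only |
| Placebo contrast | Obtainable from the MMRM | None in 17.4.3 or in the title of Table 14.2.5 |
| Declared change | Not applicable | None (4.7) |

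The method row and the last row cannot both stand. The endpoint and contrast rows show a second gap, inside the SAP: an endpoint with no described estimate.

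**2. Scale of the missing comparison**

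The protocol gives no power, effect size or SD for PANSS, so the only figure to reproduce is the number dosed. Protocol 14.1 and SAP 4.4 give 6 active and 2 placebo per cohort, with up to 5 cohorts: 5 × (6 + 2) = 40. This matches the stated maximum of 40, made up of 30 active and 10 pooled placebo.

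For one dose group against pooled placebo at one visit, with variance pooled over all groups and every dosed subject contributing:

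- SE = SD × √(1/6 + 1/n_placebo)
- df = subjects − groups
- 95% half-width = t(0.975, df) × SE

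| Cohorts | Placebo n | SE (SD units) | df | 95% half-width (SD units) |
|---|---|---|---|---|
| 5 | 10 | 0.516 | 40 − 6 = 34 | 1.05 |
| 4 | 8 | 0.540 | 32 − 5 = 27 | 1.11 |
| 3 | 6 | 0.577 | 24 − 4 = 20 | 1.20 |

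The documents give no SD of change. If it is assumed to lie between 8 and 15 points, the five-cohort half-width is 1.049 × 8 = 8.4 to 1.049 × 15 = 15.7 PANSS points.

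**3. Size of the protocol's model**

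There are six groups (five doses and pooled placebo) and four post-baseline PANSS visits (Days 8, 15, 22 and 29, protocol Table 2). This gives 6 × 4 = 24 means. An unstructured covariance adds 4 × 5 / 2 = 10 parameters, all from about 40 subjects. The model can be specified, but it needs a fallback in case it fails to converge.

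**The case against.** **Descriptive analysis suits a study of this size.** This stands. The SAP calls the analysis exploratory, the intervals would be wide, and the MMRM is large for the data. It supports choosing description, but not making that choice while SAP 4.7 denies any change.

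**Readers can recover the estimate.** This stands in part. The tabulated n, mean and SD give an unadjusted difference and interval, and someone holding the subject listing could fit a baseline-adjusted model. Neither is a planned, reported result. A later MMRM would not be wholly post hoc either, since the protocol fixes method, response and fixed effects; only the items left to the SAP are open.

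**The templates may contain the contrast.** This also stands. SAP 8 says the templates set the content of the tables, and they were not supplied. A reader might infer that the placebo-corrected estimate is certainly absent from the planned outputs. The documents show only that it is absent from the SAP text and from the table title. A column in a template would still not restore the MMRM or make SAP 4.7 accurate.

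**The protocol version may differ.** SAP 2 cites version 1.0 and amendment 2.0, and the copy reviewed has no title page to match against these. The MMRM appears in both its synopsis and its body.

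**A reader might infer that PANSS visits missed after early exit have no rule, and that the by-visit means are therefore biased.** SAP 7.8, read alone, invites this: "Missing PK data will be handled as described in Section 17 of this analysis plan". The documents do not support it. Under protocol 12.1 and 10.5.4.1, subjects who leave before Day 29 have the Day 29 assessments, including PANSS, at exit. SAP 7.3 then assigns early-termination data to the next planned visit unless that is more than 14 days away, and post-baseline PANSS visits are 7 days apart. What remains is an ambiguity: the last sentence of that rule names only PK and safety data. No dropout rate is given from which a bias could be calculated.

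**Conclusion.** The point holds. Against the protocol reviewed, SAP 17.4.3 omits a specified MMRM and SAP 4.7 is incorrect in reporting no change; confidence in both is high. The SAP text also describes no analysis for the placebo-corrected endpoint it names. Whether the planned outputs lack it too depends on the templates.

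The consequence is limited. The analysis is exploratory, and no safety, MID/MTD or escalation conclusion rests on it. With five full cohorts, a dose-versus-placebo difference would carry a 95% half-width of about 1.05 SD of change, assuming a common variance and complete data. Even the planned model is therefore likely to give imprecise estimates. The defect is an undeclared departure and an endpoint without a described estimate. It should be fixed, but it does not threaten the study's main conclusions.

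**What to change.** Before the unblinding for final analysis (SAP 5.2), correct SAP 4.7 and take one of two routes:

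- **(a) Restore the MMRM in SAP 17.4.3.** State the covariance structure, the fallback, the degrees-of-freedom method and the confidence level. Unstructured with Kenward-Roger, then simpler structures, is one reasonable choice. Add a table to Appendix 4 of LS-mean differences from pooled placebo at Days 8, 15, 22 and 29, labelled exploratory.
- **(b) Keep the descriptive analysis.** Declare and justify the departure in SAP 4.7, and add the difference from pooled placebo, with a confidence interval of stated level, to Table 14.2.5.

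Under either route, state in SAP 7.3 that the early-termination mapping covers PANSS.

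No new data are needed. Route (a) costs SAP wording, one model and one table; its drawback is fitting a large model to about 40 subjects. Route (b) costs SAP wording and added columns in one table; its drawback is losing the baseline adjustment and the likelihood-based handling of missing values that the protocol planned.

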### **18. SAFETY OUTCOMES**

Adverse events and concomitant meds summary tables will be presented by oral and injectable treatment groups in the safety population. Injection site reaction related AEs will be presented by ISAF. All other safety summary data will be presented using ISAF population. OSAF population will be used for listings. There will be no statistical comparisons between the treatment groups for safety data, unless otherwise specified with the relevant section. Summary tables will be presented by treatment (dose level of Lurasidone injectable suspension and pooled placebo).

AEs and all other safety data will be listed and summarized descriptively by treatment group (dose level of Lurasidone injectable suspension and pooled placebo) in tabular or graphical formats, as appropriate. Observed values, as well as change from baseline for clinical safety laboratories, vital signs, and ECGs will be listed and summarized descriptively in tabular formats, as appropriate. Any clinically significant results in clinical safety laboratories, vital signs, and ECGs will be listed and summarized. Frequency and severity of suicidality, based on the C-SSRS, will be listed and summarized.

#### **18.1. PRETREATMENT EVENTS AND ADVERSE EVENTS**

Pretreatment events will be recorded from the time informed consent is provided at screening until the Document:

Author:

Version Number:  
Version Date:

Final Draft  
11APR2019

Template No: CS\_TP\_BS016 Revision 4  
Effective Date: 01Apr2016

Reference: CS\_WI\_BS005

time of first lurasidone oral tablet dose administration at Day-7.

Adverse events will be collected for each subject from immediately after the first lurasidone oral tablet dose administration at Day -7 until the follow-up visit at Day 61 ( $\pm 2$ ). Adverse Events (AEs) will be coded using Medical Dictionary for Regulatory Activities (MedDRA) central coding dictionary, Version 21.0 or higher.

- Adverse Events for the Oral Lurasidone tablet period is defined as an AE that started on or after the first dose of the oral lurasidone tablet.
- Adverse Events for the double-blind Injection period is defined as an AE that started on or after the date of the double-blind injection.
- Adverse Events that started on the Oral Lurasidone tablet period and continued the double-blind injection, but the severity did not change the AE will be reported in the Oral Lurasidone tablet period. If the severity of the AE gets worse, the AE will be considered in the double-blind injection period.

AEs will be summarized by treatment and by MedDRA system organ class (SOC) and Preferred Term (PT).

An overall summary of number of subjects within each of the categories described in the sub-section below, will be provided as specified in the SAP.

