^e Subjects will restart prior medications (including antipsychotics) on Day 29 under observation of clinical site staff.

Eligible subjects will be washed out/tapered off of their current antipsychotic medications over 5 to 6 half-lives prior to Day -8 (may begin Day -19). Subjects will be monitored for safety during tapering/washout. Subjects will be admitted to the clinical site on Day -12 and are required to be inpatient until Day 15.

Subjects will receive oral lurasidone 80 mg tablets on Day -7 and Day -6 (one dose per day), and be monitored for 5 days to ensure the subject is able to tolerate lurasidone (ie, absence of moderate adverse events). Subjects who tolerate dosing with oral lurasidone 80 mg will be eligible for randomization to receive a single lurasidone injectable suspension or placebo injection on Day 1.

Subjects who are discharged after Day 15 will check into the clinical site again on Days 22 and 29 for scheduled assessments. Subjects will follow protocol procedures to remain in-clinic through Day 33 as they restart their prior medications (including antipsychotics), under observation of the Investigator/clinical site staff (ie, restabilization period).

Subjects who remained in-clinic through Day 29 will remain inpatient through Day 33 as they restart their prior medications (including antipsychotics) under observation of the Investigator/clinical site staff (ie, restabilization period).

The restabilization period may be longer and subjects may remain in-clinic, as deemed necessary by the Investigator.

Subjects who discontinue the study prior to Day 29 will undergo assessments scheduled for Day 29 at the time of discontinuation (see Table 2). Subjects who discontinue the study after Day 29 but prior to Day 61 will undergo assessments scheduled for Day 61 at the time of discontinuation (see Table 2).

Subjects who complete the study per protocol will return to the clinic for a follow-up safety assessment on Day 61 (\pm 2).

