10.5.3.8. Day 22 (Safety and Tolerability Observation)

Subjects may remain inpatient at the Investigator's discretion throughout the Treatment and Observation Period.

Subjects who have been discharged on Day 15 will have a clinic visit on Day 22.

The following study related procedures will be performed:

- Awaken Subject (daily if inpatient).
- Provide Meals (daily if inpatient).
- Obtain Vital Signs on Day 22 (approximately time-matched to the injection predose timepoint on Day 1).
- Perform 12-Lead ECG on Day 22 (approximately time-matched to the injection predose timepoint on Day 1).
- Collect Blood and Urine Samples for Clinical Laboratory Tests on Day 22 (time-matched to the injection predose timepoint on Day 1):
 - Hematology
 - Serum Chemistry
 - Urinalysis
- Obtain Blood Sample for Serum Prolactin on Day 22.
- Obtain Blood Sample for PK On Day 22.
- Administer C-SSRS on Day 22.
- Administer PANSS on Day 22.
- Schedule Next Visit.
- Discharge Subject (if clinically stable in the Investigator's opinion).
- Subject Injection Site Pain Assessment on Day 22.
- Investigator Injection Site Safety Assessment on Day 22.
- Record Concomitant Medications.
- Record Adverse Events.

10.5.4. Days 29 to 33 (End of Safety and Tolerability Observation and Beginning of Restabilization)

Subjects are required to be inpatient Days 29 to 33. Day 29 is the end of the safety and tolerability observation period for lurasidone injectable suspension/placebo injection. Day 29 is also the start of the restabilization period.

Restabilization' refers to the reintroduction of each subject's prior medications that were taken prior to entry into the study including their psychotropic medications. For early termination patients who received lurasidone dosing, following follow-up procedures they will need to be restabilized following the restabilization procedures.

Subjects who discontinue the study prior to Day 29 will undergo assessments scheduled for Day 29 at the time of discontinuation.

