## **18.2. LABORATORY EVALUATIONS**

Results from the central laboratory will be included in the reporting of this study for clinical chemistry, hematology, and urinalysis Lipid Panel, Thyroid Panel, Coagulation Panel Urine Drug Screening, Serology Panel, and Other Tests.

A list of laboratory assessments to be included in the outputs is included in appendix II/ the protocol, Section 21.

ISAF population will be used for all laboratory summaries. OSAF population will be used for the listings.

Presentations will use standard international (SI) Units

---

Document:

Author:

Version Number:  
Version Date:

Final Draft  
11APR2019

Template No: CS\_TP\_BS016 Revision 4  
Effective Date: 01Apr2016

Reference: CS\_WI\_BS005

Quantitative laboratory measurements reported as “< X”, i.e. below the lower limit of quantification (BLQ), or “> X”, i.e. above the upper limit of quantification (ULQ), will be converted to X for the purpose of quantitative summaries, but will be presented as recorded, i.e. as “< X” or “> X” in the listings.

Note that handling of retests and unscheduled measurements are included in Section 7.3 to save repetition in different sections of the SAP

The following summaries will be provided for laboratory data:

- Actual and change from baseline by visit (for quantitative measurements) and by treatment.
- Shift from baseline by treatment and visit of subject with laboratory values below, within, and above the normal range.
- Incidence of subjects with a Markedly Abnormal Post-Baseline Laboratory value (MAPLV) for select parameters by treatment.
- Actual and change from baseline for selected serum chemistry parameters (Hemoglobin, Haematocrit, Uric Acid and serum prolactin) values by visit, treatment and by gender.
- Shift from baseline by visit, treatment and by gender of subject for selected serum chemistry parameters (Hemoglobin, Haematocrit, Uric Acid and serum prolactin) below, within, and above the normal range.
- Incidence of subjects with a Markedly Abnormal Post-Baseline Laboratory value (MAPLV) for selected serum chemistry parameters (Hemoglobin, Haematocrit, Uric Acid and serum prolactin) values by treatment and by gender.
- Data listings for all laboratory parameters along with comments will be provided. Results outside of the reference range will be flagged.

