## 18.3. ECG EVALUATIONS

Results from the central ECG (Electrocardiogram) Reading Centre will be included in the reporting of this study. Safety population will be used.

ISAF population will be used for all ECG summaries. OSAF population will be used for the listings.

The following ECG parameters will be reported for this study:

- PR Interval (msec)
- QRS Interval (msec)
- QTcF Interval (msec)
- QTcB Interval (msec)
- QT Interval (msec)
- HR (bpm)
- Overall assessment of ECG (Investigator's judgment):
  - Normal
  - Abnormal, Not Clinically Significant (ANCS)
  - Abnormal, Clinically Significant (ACS)

The following summaries and listings will be provided for ECG data:

- Observed values and changes from baseline will be presented at each evaluation timepoint and by treatment. Data will be summarized using descriptive statistics (n, mean, mean, median, minimum, maximum)

Summary of ECG categories of Markedly Abnormal Criteria will be summarized by timepoint and by

---

Document:

Author:

Version Number:  
Version Date:

Final Draft  
11APR2019

Template No: CS\_TP\_BS016 Revision 4  
Effective Date: 01Apr2016

Reference: CS\_WI\_BS005

treatment in frequency tables with counts and percentages for number of subjects. This will include overall for the oral period and double-blind injection period. The overall oral period includes Day -7, Day -6, Day 1 (Predose) and Baseline and all unscheduled visits within this period. The overall double-blind (DB) injection period includes Day 1 (postdose timepoints) to Day 61 and all unscheduled visits within this period.

- Listing of Electrocardiogram clinical interpretation of ECG findings including Markedly Abnormal Criteria

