## DOUBLE-BLIND INJECTION PERIOD

START DATE	STOP DATE	ACTION
Known	Known	If start date < injection start date and after oral tablet, then not AE If start date >= injection start date, then AE
	Partial	If start date < injection start date and after oral tablet, then not AE If start date >= injection start date and after oral tablet, then AE
	Missing	If start date < injection start date and after oral tablet, then not AE If start date >= injection start date and after oral tablet, then AE
Partial, could be on or after injection start date	Known	If stop date >= injection start date, then AE
	Partial	Impute stop date as latest possible date (i.e. last day of month if day unknown or 31st December if day and month are unknown), then: If stop date >= injection start date, then AE
	Missing	Assumed AE

Document:

Author:

Version Number:  
 Version Date:

Final Draft  
 11APR2019

Template No: CS\_TP\_BS016 Revision 4  
 Effective Date: 01Apr2016

Reference: CS\_WI\_BS005

START DATE	STOP DATE	ACTION
Missing	Known	If stop date $\geq$ injection start date, then AE
	Partial	Impute stop date as latest possible date (i.e. last day of month if day unknown or 31st December if day and month are unknown), then: If stop date $<$ injection start date, then not AE If stop date $\geq$ injection start date, then AE
	Missing	Assumed AE

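### The SAP's cumulative injection-period safety tables run to Day 61 with no cut when subjects restart their prior psychotropics, so two drug exposures share one dose column

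*SAP*

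**What the plan says.** **SAP.** Section 18.1 defines injection-period events by onset alone: "Adverse Events for the double-blind Injection period is defined as an AE that started on or after the date of the double-blind injection". It has events collected "from immediately after the first lurasidone oral tablet dose administration at Day -7 until the follow-up visit at Day 61" (±2 days). The Appendix 2 date algorithm sets no upper limit either: "If start date >= injection start date, then AE". Section 18.3 states the ECG window outright: "The overall double-blind (DB) injection period includes Day 1 (postdose timepoints) to Day 61 and all unscheduled visits within this period". Sections 18.2 and 18.4 ask for incidences of markedly abnormal laboratory values (MAPLV) and vital signs (MAPVS), for example "Incidence of subjects with a Markedly Abnormal Post-Baseline Laboratory value (MAPLV) for select parameters by treatment", with no end date. Section 7.3 feeds unscheduled post-baseline values into both. The treatment columns in Appendix 1 are oral 80 mg, five injection doses and placebo. No restabilization or follow-up period is defined.

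**Protocol.** Section 10.5.4: "Day 29 is the end of the safety and tolerability observation period for lurasidone injectable suspension/placebo injection". Section 6.1 (Figure 1, footnote e): "Subjects will restart prior medications (including antipsychotics) on Day 29 under observation of clinical site staff". Section 10.5.4.1 lists the same step on Day 29. Section 9.5.1, however, does not allow prior medications until Day 30 is complete. Section 3.3 justifies two separate 28-day windows, one after injection and one after restabilization.

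**The concern.** The protocol treats the time after injection and the time after the restart as different periods. The SAP takes care to separate oral-tablet events from injection events, but it merges these two. An incidence counted to Day 61 therefore mixes about four weeks on the injection or placebo alone with about a month on each subject's own psychotropic medication as well.

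Safety by dose is the main output of this study (Protocol 14.1 and SAP 4.4 call the primary endpoints safety). The groups are small: 6 per dose and, with five cohorts, 10 pooled placebo. An event caused by a restarted drug would sit in a dose column.

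The relatedness tables do not remove it. Protocol 11.3 allows a rating of possible where concurrent drugs could explain the event, and SAP 18.1.1.2 counts possible, and also a missing rating, as related.

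**Working it through.** **1. The plan's own calendar reproduces.** 672 h / 24 + 1 = Day 29. 1440 h / 24 + 1 = Day 61. Day 61 − Day 33 = 28 days of follow-up after restabilization. 35 + 61 = 96 days, the stated maximum participation.

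**2. Share of the window from the restart on.** Visit days are from Protocol Table 2 and its footnotes. The restart is taken as Day 29, with scheduled Day 29 assessments assumed to precede it.

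| Data | Post-injection schedule | From restart on |
|---|---|---|
| Adverse-event days | Days 1–61 | Days 29–61: 33/61 = 54% |
| Chemistry, hematology, urinalysis, prolactin | Days 8, 15, 22, 29, 33, 61 | 2/6 = 33% |
| ECG, blood pressure, pulse | 6 h, 12 h, Days 3, 5, 7, 9, 11, 13, 15, 22, 29, 33, 61 | 2/13 = 15% |
| Weight | Days 29, 33, 61 | 2/3 = 67% |
| Lipid, thyroid, coagulation | Days 15, 29 | 0/2 |

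With the ±2-day visit window, the adverse-event share is 31/59 = 53% to 35/63 = 56%. If the restart waits until Day 30 is complete, it is Days 31–61, or 31/61 = 51%. PANSS and the scheduled injection-site ratings end by Day 29.

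**3. Effect on a contrast, equal added risk.** Let p be the incidence before the restart and q the chance of a new event after it, independent of earlier events and equal in both arms. The reported incidence is 1 − (1 − p)(1 − q), so the risk difference becomes (p1 − p0)(1 − q). The documents give no rates. Assume p1 = 50% on a dose and p0 = 20% on placebo:

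| q | Dose | Placebo | Difference | Ratio |
|---|---|---|---|---|
| 0 | 50% | 20% | 30 points | 2.50 |
| 0.1 | 55% | 28% | 27 | 1.96 |
| 0.2 | 60% | 36% | 24 | 1.67 |
| 0.3 | 65% | 44% | 21 | 1.48 |
| 0.5 | 75% | 60% | 15 | 1.25 |

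**4. Unequal added risk.** The same formula applies with a separate q per arm.
- q = 0.3 on the dose and 0.1 on placebo: 65% − 28% = 37 points, wider than 30.
- The reverse: 55% − 44% = 11 points.

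**5. Small counts.** With q = 0.1, the chance of at least one late event is 1 − 0.9^6 = 47% in a dose group and 1 − 0.9^10 = 65% in pooled placebo. One event moves a dose group by 1/6 = 17 points, but only if that subject is not already counted in that row.

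**The case against.** Much of the safety output is already separated in time. Laboratory values and shifts, and vital-sign and ECG values, are tabulated by visit or timepoint. ECG abnormality categories are also given by timepoint, and the overall row is an addition. Figure 14.3.1 shows adverse-event incidence by study day, and listings are chronological. This stands for those outputs, so a reader should not infer that every safety result is pooled to Day 61. For laboratory tests and vital signs the SAP never uses an injection-period label; only the cumulative MAPLV and MAPVS incidences lack a cut. Oral-period events that do not worsen also stay in the oral period. But the by-day figure has no specified breakdown by term, severity or relatedness, and listings leave the split to the reader.

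A second objection is that the SAP follows the protocol. Section 10.2.1 collects events to Day 61, Section 14.3.5.1 sets no end date, Section 6.3.2 speaks of six weeks of monitoring, and PK is sampled to 1440 h. This also stands, as a reason to keep the late data. It tells against resting the tolerability conclusion on the pre-restart period alone, since delayed depot effects could be sidelined. It is no reason to leave the two exposures unseparated.

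Third, safety comparisons are descriptive (SAP Section 18), and the Safety Review Team reviews each cohort at 14 and 28 days. No test or power is affected. A reader might infer that dose escalation or the tolerated-dose decision is compromised. The documents do not support that, because both reviews are scheduled no later than the restart.

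**Conclusion.** The point holds for four sets of cumulative outputs: the injection-period adverse-event tables, the overall ECG markedly-abnormal row, and the MAPLV and MAPVS incidences. In these, post-restart events are reported under a lurasidone dose or placebo with no way to tell them apart within the table. The 54% applies to adverse-event days only; the other shares are in the working, and weight is the most exposed.

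It is tempting to conclude that the contrast with placebo must be diluted. That needs equal added risk in both arms. If depot drug is still present, late events may reflect both drugs and the bias can go either way. The size is unknown: every event rate above is assumed, and subjects resume medication on which they were required to be stable. The finding is a reporting weakness worth correcting in the final analysis, not a flaw in the conduct of the study.

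**What to change.** In SAP 18.1 to 18.4 and Appendix 2, for these cumulative incidence tables only, show by dose and pooled placebo:

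- (a) injection to the subject's recorded first dose of restarted psychotropic medication;
- (b) that restart to Day 61;
- the Day 1–61 total alongside.

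Keep all late data, and interpret (a) and the total together. Carry an event into (b) by the worsening rule that Section 18.1 already uses between the oral and injection periods.

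Use each subject's actual restart date and time, so that pre-restart Day 29 assessments stay in (a) and early terminators are cut at their own restart. Protocol 9.5 lists the medication start date but not the time. Where only the date is held, keep scheduled Day 29 assessments in (a), and fix in advance where events starting on that date are counted.

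Protocol Sections 6.1 and 10.5.4.1 (Day 29) and 9.5.1 (Day 30 completed) must be reconciled before the cut is programmed.

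The cost is SAP and table-shell wording and a few more columns. Onset and medication start dates are already collected.
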